11.2. Procedures for recording adverse events

AEs will be reported using the following guidance:

- (a) All AEs occurring after enrolment until study completion or withdrawal, that are observed by an investigator/member of the health care team, or that are reported by the participant, will be detailed in the Case Report Form (CRF), whether or not attributed to the study.
- (b) Pre-existing medical conditions (present before start of the AE collection period) are considered “concurrent medical conditions” and should not be recorded as AEs. However, if the participant experiences a worsening or complication of such a condition, the worsening or complication should be recorded as an AE. Investigators should ensure that the AE term recorded captures the change in the condition (e.g., “worsening of”)
- (c) Each AE should be recorded to represent a single diagnosis. Accompanying signs or symptoms (including abnormal laboratory values) should NOT be recorded as additional AEs.
- (d) Changes in laboratory values and vital signs are only considered to be AEs if they are judged to be clinically significant, e.g., if some action or intervention is required. If abnormal laboratory values or vital signs are the result of pathology for which there is an overall diagnosis, the diagnosis only should be reported as one AE.
- (e) AEs considered related to the study as judged by a medically qualified investigator or the sponsor, will be followed either until resolution, or the event is considered stable.

11.3. Reporting procedures for Serious Adverse Events

All SAEs will be recorded from the point of enrolment until the 14-day follow-up period, outlined in trial timeline. Follow-up information will be provided as necessary. A member of the site research team will obtain information from the hospital or clinic to enable reporting to the sponsor and the HRECs. All SAEs will require a report to be prepared by a suitably qualified medical practitioner for the principal investigator. All SAEs must be reported on the SAE reporting form and emailed to the sponsor within one working day of the site study team becoming aware of the event. In addition, all SAEs must be reported to the approving HREC within 72 hours of the study team’s awareness of the event. Additional and further requested information (follow-up or corrections to the original case) will be detailed on a new SAE Report Form and emailed to the sponsor. Once the SAE Notification Form is received by the sponsor, the PI (or delegate) will investigate the expectedness of the event and forward the report to the Independent Safety Monitor (ISM). All serious, related, and unexpected (SUSARs) SAEs will be reported to the TGA by the sponsor.

As per the 2016 updated NHMRC position statement on safety monitoring of clinical trials involving therapeutic goods, AEs, SAEs, external SUSARs, and SUSARs six-monthly line listings to the HREC will no longer be reported. Instead, the sponsor will provide an annual safety report to the HREC in lay language. SUSARs which occur on site and significant safety issues will still be reported to the institution (within 72 hours). A figure outlining the safety reporting flowchart is attached as Appendix 2.

11.4. Independent Safety Monitor

The ISM should receive full details of all SAEs. SAEs should be reported to the ISM within three days of the sponsor receiving notification of the event. A list of all safety events will be provided to the ISM at the end of each month of the study period; the ISM can request further investigation or interim analysis of any/all events, at his/her discretion. The ISM will discuss any safety concerns with the PI at any point throughout the study period.

11.5. Principal Investigator's responsibilities

The PI or delegate should:

- (a) Capture and assess all AEs that occur at the site as required and in accordance with the protocol.
- (b) Report to the sponsor within 24 hours of becoming aware of the event:
 - a. all SAEs, except those that are identified in the protocol as not needing immediate reporting.
 - b. any occurrences of congenital anomaly/birth defect arising from any pregnancy of a participant (or partner).
 - c. all urgent safety measures instigated by the site.
- (c) Report to the sponsor as specified in the protocol:
 - a. all safety-critical events.
 - b. any additional requested information relating to reported deaths.
- (d) Report to the institution within 72 hours of becoming aware of the event:
 - a. all significant safety issues.
 - b. SUSARs arising from the local site (reported when, in the investigator's judgement, a SUSAR has occurred. The investigator should not unblind the SUSAR for the purposes of reporting to their institution).

11.6. Causality

The relationship of each adverse event to the trial medication must be determined by a medically qualified investigator according to the following definitions:

Related: The adverse event follows a reasonable temporal sequence from trial medication administration. It cannot reasonably be attributed to any other cause.

Probably related: The adverse event follows a reasonable temporal sequence from trial medication administration. Although one or more other causes can be reasonably attributed, it is most reasonably attributed to the study medication.

Possibly related: The adverse event follows a reasonable temporal sequence from trial medication administration, but it can be more reasonably attributed to another cause.

Not Related: The adverse event is probably produced by the participant's clinical state or by other modes of therapy administered to the participant.

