6.14. Potential risks and benefits of BPG to humans

6.14.1. Potential risks

AEs to Bicillin® L-A, are uncommon. Despite being the only current form of BPG licenced for use in Australia, there have been episodes of 'stockouts'.^{33,71} During these periods, a powdered form of BPG was used. A search of the Database of Adverse Event Notifications – from 1st January 1971 through to 18th February 2017 for all types of benzathine penicillin reveals only 22 case reports, 13 in which Bicillin® L-A was the only medication administered. There were no adverse reactions noted for the powdered BPG used during stockouts.⁴² Prior to 1995, Bicillin® L-A was only available in Australia in the 2.4 MIU unit prefilled syringe. It required clinicians to either use half of the dose or decant the Bicillin into a secondary syringe prior to administration.³³ Since 1995, there have been 11 adverse reactions reported to the TGA, seven in which Bicillin® L-A was the only administered medication. Of the seven, one reported a cardiac arrest, hypotonia, and seizure. One reported injection site reaction with abscess, four reported injection site reaction, one reported gait disturbance, three reported pyrexia, one reported otitis media, and one reported erythema, pain, rash, and swelling. From the period September 1997 through to May 2014, a total of 20,641 prescriptions were filled for Bicillin® L-A, representing a total of 206,410 doses prescribed.⁷¹ This corresponds to an almost zero absolute risk of reaction. BPG is a commonly used medication; the reported side effects/adverse drug reactions are mentioned in the product information sheet in Appendix 1.⁷²

Intramuscular injection is a frequently-used route of parenteral drug administration. In IM injections, the skin is broken, SC tissue is traversed, and medication injected into the muscle. IM injections have been shown to have increased absorption into systemic circulation compared to SC injections.⁷³ The most common side effects are pain, redness, and localised swelling. There is a small risk of: infection, damage to muscle, nerve, skin necrosis, inadvertent vascular damage/injection, anaphylactic reaction, and death. Most of the serious complications involving tissue necrosis will resolve with conservative management; a small percentage of severe cases may require medical procedures e.g. fasciotomy, if complicated by compartment syndrome.^{45,51} As with any drug, anaphylactic reactions can cause death in its most severe cases.

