7.4. Secondary endpoints

- (a) Pain scores related to administration of Bicillin® L-A for the SC and IM routes.
- (b) Defined AEs related to SC and IM routes of administration of Bicillin® L-A.
- (c) Time above the MIC for Bicillin® L-A administered via the SC and IM routes.

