11.1. Definitions

Table 5: List of definitions for assessment of safety

Adverse Event (AE)	Any untoward medical occurrence in a patient or clinical trial participant administered a medicinal product and that does not necessarily have a causal relationship with this treatment. An AE can be any unfavourable and unintended sign (including an abnormal laboratory finding), symptom, or disease temporally associated with the use of the study medication, whether or not considered related to the study medication.
Adverse Reaction (AR)	Any untoward and unintended response in a participant to an IMP related to any dose administered to that participant. Comment: All adverse events judged by either the reporting investigator or the sponsor as having a reasonable possibility of a causal relationship to an IMP would qualify as adverse reactions. The expression ‘reasonable causal relationship’ means to convey, in general, that there is evidence or argument to suggest a causal relationship.
Safety Critical Adverse Events	Adverse events and/or laboratory abnormalities identified in the protocol as critical to safety evaluations that should be reported to the sponsor according to the reporting requirements specified in the protocol.
Serious Adverse Event (SAE)/Serious Adverse Reaction (SAR)	Any adverse event/adverse reaction that: 
 (a) results in death (b) is life-threatening (c) requires inpatient hospitalisation or prolongation of existing hospitalisation (d) results in persistent or significant disability/incapacity (e) is a congenital anomaly or birth defect 
Note: Life-threatening in the definition of a serious adverse event or serious adverse reaction refers to an event in which the participant was at risk of death at the time of the event. It does not refer to an event that hypothetically might have caused death if it were more severe.
 
Note: Medical and scientific judgement should be exercised in deciding whether an adverse event/reaction should be classified as serious in other situations. Important medical events that are not immediately life-threatening or do not result in death or hospitalisation, but may jeopardise the participant or may require intervention to prevent one of

	the other outcomes listed in the definition above should also be considered serious.

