11.7. Expectedness

Expectedness will be determined according to the product information sheet. Any SAE considered to be unexpected and related to the study drug will be reported to the TGA.

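### Endpoint 7.4(b) counts adverse events related to route, but 11.6 records causality only against the drug, on a scale that overlaps and does not match Table 5

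*Protocol*

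**What the plan says.** The protocol uses relatedness with three different objects.

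- **Route.** Section 7.4(b) lists as a secondary endpoint "Defined AEs related to SC and IM routes of administration" of the product.
- **Product or trial medication.** The secondary safety aim in the synopsis and in 5.2 is about AEs related to the product, compared by route. Section 11.6 says "The relationship of each adverse event to the trial medication must be determined by a medically qualified investigator".
- **Study.** Section 11.2(e) follows up AEs considered related to the study.

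The safety outcome in the synopsis uses no relatedness at all. It compares the type, number and severity of AEs after each route.

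Section 11.6 has four levels. *Related* requires a plausible time sequence and adds: "It cannot reasonably be attributed to any other cause". *Probably related* reads: "Although one or more other causes can be reasonably attributed, it is most reasonably attributed to the study medication". *Possibly related* keeps the time sequence, "but it can be more reasonably attributed to another cause". *Not Related* covers events probably due to the participant's clinical state or to other therapy, with no condition on timing.

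For reporting, 11.7 says "Any SAE considered to be unexpected and related to the study drug will be reported to the TGA", and 11.3 uses the word related in the same way. Table 5 sets a different test for an adverse reaction: AEs judged as "having a reasonable possibility of a causal relationship to an IMP would qualify as adverse reactions". It defines a SUSAR as an adverse reaction that is serious and unexpected, and 11.8 sends all SUSARs to the TGA.

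**The concern.** The trial compares two ways of giving one product at one dose. What differs between the periods is where the depot is placed and how the needle is used. A causality question about the medication alone does not ask about that difference, although the endpoint is worded in terms of it. If the safety comparison is restricted to related AEs, as 5.2 and 7.4(b) say, an injury caused by the injection rather than by penicillin may fall outside it.

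The scale adds to this. If two investigators can correctly give one event different codes, or if related means one thing in 11.6 and another in Table 5, the related subset is not well defined. At stake are a secondary endpoint, the tolerability hypothesis in 7.2, and a consistent rule for what goes to the TGA. The primary PK endpoint is not touched.

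**Working it through.** There is no stated figure to reproduce. The check sets the sections side by side.

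**1. Does the causality rule measure the endpoint?** Section 10.6 gives the same product, dose and volume (1016.6 mg, 1.2 MIU, 2.3 mL) for both routes. The technique differs: 90° with a Z-track and 8 to 10 aliquots for IM, and 45° for SC. None of the four levels in 11.6 names the injection, needle or route. Yet 6.14.1 says of IM injection: "There is a small risk of: infection, damage to muscle, nerve, skin necrosis, inadvertent vascular damage/injection, anaphylactic reaction, and death". Of these seven items, at least four (infection, and muscle, nerve and vascular damage) can come from the needle or the injection rather than from penicillin. Such an event best fits *Possibly related*, because another cause is more reasonable. *Not Related* does not describe it well, since the trial injection is neither the participant's clinical state nor another therapy. Whether *Possibly related* counts as related for 7.4(b) is not stated. So the event can be left out, but need not be.

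**2. Are the levels distinct?** *Related*, *Probably related* and *Possibly related* are ordered and separate. *Possibly related* and *Not Related* are not. Take an event soon after the injection that is probably due to an intercurrent illness. The timing fits and another cause is more reasonable, so it is *Possibly related*. It is also probably produced by the clinical state, so it is *Not Related*. One pair of levels overlaps.

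**3. Does related mean the same thing throughout?** Take an unexpected SAE coded *Probably related*.

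| Reading | Result |
|---|---|
| Table 5 with 11.8 | Reasonable possibility, so an adverse reaction, so a SUSAR, so reported to the TGA |
| 11.3 and 11.7, with related taken as the 11.6 level *Related* | Another cause is reasonable, so not *Related*, so not reported under these sections |

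The second reading is literal but not forced. The protocol does not say which levels count.

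**4. How much could the coding matter?** Suppose that all 15 participants receive both injections. If one participant's only event on a route moves into or out of the related set, that route's proportion of participants with a related AE changes by 1/15 = 6.7 percentage points. Two such participants change it by 2/15 = 13.3 points. This shows sensitivity only; the protocol gives no expected event rate.

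**The case against.** The strongest reply is that little is lost in practice, and much of it stands.

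- All AEs go into the CRF whether or not attributed to the study (11.2(a)), so a comparison of all AEs by route stays available. Pain scores, ultrasound changes and skin irritation are assessed separately and do not pass through 11.6. A reader might infer that the rule removes the events that differ by route. It does not; it can only affect the related subset.
- A reader might infer that procedure harms are lost from SUSAR reporting. That is not a defect: a SUSAR is by definition a reaction to the IMP. All SAEs reach the sponsor, the HREC and the safety monitor whatever their causality, and Table 5 names an SAE associated with trial procedures as an example of a significant safety issue.
- A reader might infer that probable reactions go unreported. Table 5 with 11.8 makes them reportable; the conflict arises only on the literal reading.
- The product information lists many injection-site and neurovascular reactions, and 11.6 times its positive levels from administration of the medication. Some procedure harms may therefore be coded as drug-related.
- Haematoma might be added to the needle harms named in 6.14.1, but it is not in that list.
- Which codes enter an AE table is commonly left to the SAP, which is not shown.

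The last reply does not go far enough. A SAP can choose among codes, but it cannot recover a judgement on route or procedure that was not collected. Nor can it settle a conflict between 11.3 or 11.7 and Table 5 over expedited reporting.

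**Conclusion.** The point holds as a mismatch of definitions. The rule in 11.6 does not measure the endpoint in 7.4(b), one of its boundaries overlaps, and its *Related* level is narrower than the Table 5 test for an adverse reaction. The effect is limited to the related-AE comparison by route and to consistency in the reporting text. No recorded AE disappears, and the synopsis outcome is unaffected because it has no causality filter.

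The conclusion assumes that the safety comparison follows 5.2 and 7.4(b) rather than the synopsis outcome, and that the CRF collects causality as 11.6 words it. If the analysis already compares all AEs by route, only the scale and reporting faults remain. This is a cheap improvement and not a threat to the trial's main conclusion.

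**What to change.** 1. In 5.2 and 7.4(b), and in the matching aim in the synopsis, base the route comparison on all AEs following each route, as the synopsis outcome does. This also frees it from a causality judgement whose assessor is not required to be blind to route (10.1 blinds the participant).
2. Add a separate CRF field for relationship to the injection procedure or route. Keep it apart from IMP causality. A single combined judgement would make a pure needle injury related to the study drug under 11.7, against Table 5.
3. Reword *Possibly related* and *Not Related* so that no event can meet both.
4. State which 11.6 levels count as related in 11.2(e), 11.3 and 11.7, consistent with the reasonable-possibility test in Table 5, and say in 11.2(e) what relatedness to the study covers.

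The cost is one more CRF field, some protocol wording, and slightly more events tabulated on both routes.

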11.7. Expectedness

Expectedness will be determined according to the product information sheet. Any SAE considered to be unexpected and related to the study drug will be reported to the TGA.

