7.5. Study stopping rules

Individual subjects will be stopped from continuing in the trial if they:

- (a) display signs or symptoms of a penicillin allergy.
- (b) have a serious adverse reaction.
- (c) request discontinuation.

An individual subject who wishes to stop the trial after first dosing will be withdrawn from the study and followed up as per the withdrawal section 8.5.

The trial can be stopped at any stage at the discretion of:

- (a) the Principal Investigator (PI)
- (b) the study sponsor
- (c) suspected unexpected serious adverse reaction (SUSAR), after discussion with the ethics committee

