10.4.2. Formulation

BPG is comprised of a suspension of two benzylpenicillin molecules and a benzathine molecule forming a white crystalline powder that is very slightly soluble in water and sparingly soluble in alcohol. It is approved for deep IM injection. Bicillin® L-A refers to the resultant aqueous suspension which also contains a citrate buffer and, as weight/volume, approximately 0.5% lecithin, 0.6% carboxymethylcellulose, 0.6% povidone, 0.1% methylparaben, and 0.01% propylparaben. Bicillin® L-A is an opaque, viscous suspension. In Australia, it is available in 2.3ml corresponding to 1,200,000 units of penicillin G. Administration of Bicillin® L-A 1,200,000 units via deep IM injection results in prolonged serum concentrations of the active metabolite; penicillin G levels of 2.25ng/mL may still be detectable for four weeks.

See PIS for additional information.

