Significant Safety Issue (SSI)	
A safety issue that could adversely affect the safety of the participants or materially impact on the continued ethical acceptability or conduct of the trial.
 
e.g.: A SAE that could be associated with the trial procedures and that requires modification of the conduct of the trial.
 
A hazard to the patient population, such as lack of efficacy of an IMP used for the treatment of a life-threatening disease.
 
A major safety finding from a newly completed animal study (such as carcinogenicity).
 
A temporary halt/termination of a trial for safety reasons.
 
Recommendations of the safety monitor, where relevant for the safety of the participants, such as an increase in frequency or severity of an expected adverse reaction.
 
Single case events (e.g. toxic epidermal necrolysis, agranulocytosis, hepatic failure) that lead to an urgent safety measure.

Suspected Unexpected Serious Adverse Reaction (SUSAR)	
An adverse reaction that is both serious and unexpected.
 
A serious adverse reaction, the nature and severity of which is not consistent with the information about the medicinal product in question set out in reference safety information - summary of product characteristics relating to the trial in question.

Unexpected Adverse Reaction (UAR)	
An adverse reaction, the nature or severity of which is not consistent with the Reference Safety Information (RSI).
 
Note: The RSI should be contained in the Investigator's Brochure for an unapproved medicinal product or Product Information (or another country's equivalent of the Product Information) for an approved medicinal product.

Urgent Safety Measure (USM)	
A measure required to be taken in order to eliminate an immediate hazard to a participant's health or safety.
 
Note: This type of significant safety issue can be instigated by either the investigator or sponsor and can be implemented before seeking approval from Human Research Ethics Committees (HRECs) or institutions.

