20.1. APPENDIX 1: Product information: Bicillin® L-A

PRODUCT INFORMATION

[figure not shown]
BICILLIN[®] L-A Suspension for Injection (Benzathine Benzylpenicillin tetrahydrate) for deep IM injection only

NAME OF THE MEDICINE

BICILLIN L-A 1,200,000 Units/ 2.3 mL pre-filled syringe with needle, containing Benzathine Benzylpenicillin tetrahydrate 1016.6 mg / 2.3 mL.

BICILLIN L-A (sterile benzathine benzylpenicillin suspension) is chemically designated as (2S,5R,6R)-3,3-dimethyl-7-oxo-6-(2-phenylacetamido)-4-thia-1-azabicyclo[3.2.0]heptane-2-carboxylic acid compound with *N,N'*-dibenzylethylenediamine (2:1), tetrahydrate.

Its chemical structure is as follows:

Chemical Formula: (C₁₆H₁₈N₂O₄S)₂·C₁₆H₂₀N₂·4H₂O

Molecular Weight: 981.18

CAS Number: 41372-02-5

DESCRIPTION

Benzathine benzylpenicillin occurs as a white or almost white powder. It is very slightly soluble in water, freely soluble in dimethylformamide and in formamide, slightly soluble in ethanol (96 per cent).

BICILLIN L-A contains benzathine benzylpenicillin (the benzathine salt of benzylpenicillin) in aqueous suspension with sodium citrate buffer and water for injection; and as w/v, approximately 0.5% lecithin, 0.5% carmellose sodium, 0.6% povidone, 0.1% methyl hydroxybenzoate and 0.01% propyl hydroxybenzoate.

BICILLIN L-A suspension in the disposable pre-filled syringe formulation is viscous and opaque.

PHARMACOLOGY

Microbiology

Benzylpenicillin exerts a bactericidal action against penicillin-sensitive micro-organisms during the stage of active multiplication. It acts through the inhibition of biosynthesis of cell-wall peptidoglycan, rendering the cell wall osmotically unstable. It is not active against the penicillinase-producing bacteria or against organisms resistant to beta-lactams because of alterations in the penicillin-binding proteins.

The following *in-vitro* data are available but the clinical significance is unknown. Benzylpenicillin exerts high *in vitro* activity against Staphylococci (except penicillinase-producing strains), Streptococci (Groups A, C, G, H, L and M) and Pneumococci. Other organisms sensitive to benzylpenicillin are: *Neisseria gonorrhoea*, *Corynebacterium diphtheria*, *Bacillus anthracis*, Clostridia spp, *Actinomyces bovis*, *Streptobacillus moniliformis*, *Listeria monocytogenes* and *Leptospira* spp. *Treponema pallidum* is extremely sensitive to the bactericidal action of benzylpenicillin.

Pharmacokinetics

Absorption

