Injection Site: Injection site reactions (including pain, inflammation, lump, abscess, necrosis, oedema, haemorrhage, cellulitis, hypersensitivity, atrophy, ecchymosis, and skin ulcer); neurovascular reactions (including warmth, vasospasm, pallor, mottling, gangrene, numbness of the extremities, cyanosis of the extremities, and neurovascular damage).

Metabolic: Elevated BUN, creatinine, and SGOT.

Musculoskeletal: Joint disorder; periostitis; exacerbation of arthritis; myoglobinuria; rhabdomyolysis.

Nervous System: Nervousness; tremors; dizziness; somnolence; confusion; anxiety; euphoria; transverse myelitis; seizures; coma.

A syndrome manifested by a variety of CNS symptoms such as severe agitation with confusion, visual and auditory hallucinations, and a fear of impending death (Hoigne's syndrome), has been reported after administration of benzylpenicillin procaine and, less commonly, after injection of the combination of benzylpenicillin benzathine and benzylpenicillin procaine. Other symptoms associated with this syndrome, such as psychosis, seizures, dizziness, tinnitus, cyanosis, palpitations, tachycardia, and/or abnormal perception in taste, also may occur.

Respiratory: Hypoxia; apnoea; dyspnoea.

Skin: Diaphoresis.

Special Senses: Blurred vision; blindness.

Urogenital: Neurogenic bladder; haematuria; proteinuria; renal failure; impotence; priapism.

DOSAGE AND ADMINISTRATION

Use a concentration of 442 mg/mL when measuring part doses. The quantity of benzathine benzylpenicillin is based on 1,200 Units/mg potency.

Streptococcal (Group A) upper respiratory infections (for example, pharyngitis)

A single injection of 1,200,000 Units for adults.

A single injection of 900,000 Units for older children.

A single injection of 300,000 to 600,000 Units for infants and for children under 27 kg.

Venereal infections

Syphilis - Primary, secondary and latent - 2,400,000 Units (1-dose). Late (tertiary including neurosyphilis) - 2,400,000 Units at 7-day intervals for three doses.

Version: pfpbaci10917

Superseded: pfpbaci10317
Page 7 of 9

Congenital (with normal CSF) - under 2 years of age: 50,000 Units/kg body weight; ages 2-12 years; adjust dosage based on adult dosage schedule.

Yaws, bejel and pinta - 1,200,000 Units (single injection).

Prophylaxis - for rheumatic fever and glomerulonephritis

Following an acute attack, benzathine benzylpenicillin (parenteral) may be given in doses of 1,200,000 Units once a month or 600,000 Units every 2 weeks.

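### Section 11.7 judges expectedness after SC injection against an IM-only product information that already lists serious injection-site reactions, and Table 5 defines a SUSAR in two conflicting ways

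*Protocol*

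**What the plan says.** Protocol section 11.7 sets one standard for both routes: "Expectedness will be determined according to the product information sheet". Its next sentence sends any SAE judged unexpected and related to the study drug to the TGA.

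The product information in Appendix 1 is titled "Suspension for Injection (Benzathine Benzylpenicillin tetrahydrate) for deep IM injection only". Section 10.4.2 says the same of the product: "It is approved for deep IM injection". Under adverse effects, the sheet lists "Injection site reactions (including pain, inflammation, lump, abscess, necrosis, oedema, haemorrhage, cellulitis, hypersensitivity, atrophy, ecchymosis, and skin ulcer". The same entry goes on to neurovascular reactions, gangrene among them.

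Table 5 (section 11.1) defines an unexpected adverse reaction as "An adverse reaction, the nature or severity of which is not consistent with the Reference Safety Information (RSI". Its SUSAR entry has two sentences. The first requires a reaction to be serious and unexpected. The second reads "A serious adverse reaction, the nature and severity of which is not consistent with the information".

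Section 7.5 gives three grounds on which the whole trial can be stopped: the discretion of the principal investigator, the discretion of the sponsor, and, as item (c), "suspected unexpected serious adverse reaction (SUSAR), after discussion with the ethics committee".

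**The concern.** SC injection is the experimental route. Section 6.9 says that no human study has compared routes of administration for BPG, and the reference sheet describes deep IM use. Nothing in the protocol says how a term listed there is to be judged when the event follows an SC injection.

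An assessor who applies 11.7 as written to skin necrosis after an SC injection finds necrosis in the list and has a textual basis for calling it expected. The event would then stay outside the rules that depend on unexpectedness, although local tolerability of this route is one of the things the trial is run to learn. The two Table 5 definitions add a separate problem: they can give different answers for the same event.

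**Working it through.** No arithmetic is needed beyond one count, so this is a comparison of texts.

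**Step 1: does the reference cover the route?** Table 5 lets the product information serve as reference safety information for an approved product. The product is registered, but the approved route is deep IM. The sheet holds no SC reference, and 11.7 names no other source.

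**Step 2: are serious local reactions already listed?** Abscess, necrosis, cellulitis, skin ulcer and gangrene all appear under the injection-site entry. Of the SC harms named in section 6.14.1, calcific granuloma and fat necrosis are not named in the sheet. Its nearest terms are the general ones, lump and necrosis.

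**Step 3: which rules depend on expectedness?**

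| Rule | Section | Depends on expectedness? |
|---|---|---|
| Report to the TGA | 11.3, 11.7, 11.8 | Yes |
| SUSAR report to the institution | 11.3, 11.5(d) | Yes |
| Event-named ground for stopping the trial | 7.5(c) | Yes |
| All SAEs to sponsor (one working day) and HREC (72 hours) | 11.3 | No |
| All SAEs to the independent safety monitor | 11.4 | No |
| Individual stop after a serious adverse reaction | 7.5 | No |
| Trial stop at the discretion of principal investigator or sponsor | 7.5(a), (b) | No |
| Significant safety issue to the institution | Table 5, 11.5(d) | No |

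**Step 4: run serious, related SC reactions through the definitions.**

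| Compared with the sheet, the reaction differs in | Unexpected (Table 5)? | SUSAR, first sentence? | SUSAR, second sentence read literally? |
|---|---|---|---|
| neither nature nor severity | No | No | No |
| one of the two only | Yes | Yes | No |
| both | Yes | Yes | Yes |

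The first row is the route problem: a listed local reaction is measured against IM experience and drops out of all three dependent rules. The second row is the wording problem. The TGA duty survives there, because the second sentence of 11.7 turns on unexpectedness alone. Whether the 7-day and 15-day limits in 11.8, the SUSAR line in 11.5(d) and 7.5(c) apply depends on which sentence of the SUSAR entry is followed.

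**Step 5: exposure.** 15 participants × 1 SC injection each = at most 15 SC injections. Section 8.5.3 allows replacement only before the first injection, so the number cannot grow.

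**The case against.** The strongest reply has four parts.

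- **The reference follows the protocol's own rule.** Table 5 names the product information for an approved product, and this product is approved. That explains the choice, but the approval does not extend to the SC route, and the protocol is silent on what follows from that.
- **Expectedness is a judgement, not a word match.** Section 11.3 has the principal investigator or a delegate investigate it for each SAE. That person could decide that an SC reaction differs in nature or severity from what an IM sheet describes. This stands. A reader might infer that a serious SC reaction could almost never become a SUSAR; the documents do not establish that. They show only that the text permits an expected classification and gives no guidance against it.
- **Most oversight is independent of expectedness.** This stands too. A reader might infer that safety monitoring of the SC route is disabled, but the second half of the Step 3 table shows otherwise. Table 5 even counts a safety-monitor recommendation about more frequent or more severe expected reactions as a significant safety issue. Section 11.9 separately halts further injections after anaphylaxis until the principal investigator has been contacted. None of these paths, however, sends a reaction classed as expected to the TGA.
- **The overlap between risks and listed terms can mislead.** The general injection risks in section 6.14.1 (infection, nerve damage, skin necrosis and so on) find counterparts in Appendix 1. That paragraph describes IM injection, so finding its risks in an IM document says nothing about SC.

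The *and*/*or* mismatch could also be read as a slip, with the first sentence of the SUSAR entry governing. That is a reasonable reading, but the second sentence still says something different.

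**Conclusion.** The point holds in a limited form. Section 11.7 applies an IM-only reference to the SC route without saying so. A serious related injection-site reaction after SC injection may therefore be classed as expected and miss TGA reporting, the SUSAR line of institution reporting and the ground in 7.5(c). Table 5 contradicts itself on what a SUSAR is, whatever the route.

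The size is three dependent rules and at most 15 SC injections. No event rate can be attached, because the documents give none for SC BPG. The conclusion assumes that an assessor follows 11.7 and the list in Appendix 1 as written; one who gives weight to the route could reach the opposite classification. That two careful assessors could differ is itself the reason to amend.

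It does not extend to systemic reactions. Anaphylaxis is not specific to a route: Appendix 1 reports it even with oral penicillins. Treating every related serious reaction after SC injection as unexpected would therefore go too far. It would also widen a trial-stopping ground for one route only.

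**What to change.** 1. In 11.7, add one sentence: for reporting purposes, a listing in the IM-only product information does not by itself make a serious related injection-site reaction after SC injection expected.
2. In Table 5, use *nature or severity* in both the unexpected-reaction and the SUSAR definitions, so that the two sentences of the SUSAR entry agree.
3. Have the sponsor reconcile 7.5(c) with the revised definition. This review takes no position on what that stopping ground should be.

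The cost is two sentences in a protocol amendment and possibly a few additional expedited reports. No data collection, sample size or analysis changes.
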